6.3 Analysis Sets

The **Enrolled Set** includes all patients who passed screening irrespective of whether they received the study treatment.

The **Completer Analysis Set** (CAS) includes all randomised patients who complete all treatment periods.

The **Full Analysis Set** (FAS) includes all randomised patients with sufficient data collected after intake of study treatment to compute the pharmacodynamics parameters on at least two treatment periods. Patients will be analysed according to the treatment they are assigned to at randomisation, irrespective of what treatment they actually received.

The **Safety Analysis Set** (SAF) consists of all patients who take at least one administration of study treatment. Patients will be analysed according to the treatment actually taken.

The **Pharmacokinetic (PK) Set** will consist of those patients in the SAF who have at least one pre-dose and one post-dose RPL554 PK concentration and with sufficient data to calculate PK parameters. Patients will be analysed according to the treatment actually taken.

The list of patients included in the FAS, CAS, SAF and PK will be agreed prior to database lock once all study data are available.

6.4 Data presentations

The data will be summarised in tabular form by treatment group apart from disposition of patients, background and demographic characteristics which will be summarised by treatment sequence and overall patients.

Only scheduled post-baseline laboratory, vital signs and ECG values will be tabulated. Post-baseline repeat/unscheduled assessments will be disregarded, although they will be listed and in particular all clinically significant values will be noted.

All listings apart from eligibility and analysis sets will be based on SAF. Eligibility and analysis sets will be listed using the enrolled set. Listings will be sorted by treatment sequence, patient number and date/time of assessment. Treatment sequences will be presented in the following order:

- Placebo RPL554 1.5 mg RPL554 6 mg
- RPL554 1.5 mg RPL554 6 mg Placebo
- RPL554 6 mg Placebo RPL554 1.5 mg
- RPL554 6 mg RPL554 1.5 mg Placebo
- RPL554 1.5 mg Placebo RPL554 6 mg
- Placebo RPL554 6 mg RPL554 1.5 mg

Graphical presentations of the data will also be provided where appropriate.

Disposition of patients will be summarised using the enrolled set. Background and demographic characteristics will be summarised using the SAF. The primary efficacy endpoints will be summarised using the FAS and CAS. Secondary endpoints will be summarised using the FAS. Protocol deviations, prior/concomitant medications and safety will be summarised using the SAF.

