4.3 Removal of Patients from Therapy or Assessment

Investigators have the authority to ask for the withdrawal of a patient at any time for medical or non-compliance reasons. Should the Investigator decide it is necessary to withdraw any patient for specific reasons, this should be recorded in writing and transmitted to the patient in question. Such reasons for withdrawal are expected to be medical or related to lack of co-operation by the patient.

If a patient withdraws following randomisation, every attempt should be made to contact the patient to determine the reason for withdrawal and to complete the recording of any available efficacy data and all adverse event data. If a patient agreed to enter the study and signed a consent form but withdrew from the study, or was withdrawn from the study, without receiving any study treatment, no further follow-up is necessary.

End of study visits will occur at 4 to 10 days after completing Day 4 of Treatment Period 3. All withdrawn patients will follow this routine unless it is considered by the Investigator that they require greater medical supervision and/or investigations and in which case an unscheduled visit prior to and in addition to the scheduled follow up visit may be performed. Patients who do not complete all treatment periods should have an end of study visit.

If a patient decides to withdraw voluntarily, or is withdrawn by the Investigator responsible at any time, the reasons for withdrawal and results of all relevant tests will be recorded in the electronic case report form (eCRF). Patients who withdraw may be replaced.

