7.4.2 Laboratory Safety Tests

In addition to the laboratory tests detailed in Section 7.4.2.1 to Section 7.4.2.3, unscheduled and/or repeat testing may be performed at the discretion of the Investigator. Any additional laboratory results will also be merged into the final database. Laboratory results will be provided to the Investigator for each patient and each visit. The Investigator should assign whether each abnormal result is not clinically significant or a clinically significant by manually annotating a print out of the results.

Samples will be taken and handled according to the laboratory manual and analysed at an approved Local Laboratory.

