6.2 Derived data

• Definition of baseline

Baseline is defined as the last non-missing value (including scheduled and unscheduled assessments) prior to the patient receiving study treatment for each of the respective study treatments.

For ECG and vital signs, time-matched baselines from Day 1 of each Treatment Period will be used for the analysis of data.

Incomplete dates

For calculation purposes, incomplete dates will be completed using worst case. Further details are detailed in the relevant sections as required.

• Non-numeric values for numeric variables

In the case where the result of a variable is recorded as ">x", " \ge x", "<x" or " \le x", then for analysis purposes a value of x will be taken. Where a range of values is quoted the midpoint of the range will be taken.

• Methods for handling withdrawals and missing data

Patients withdrawn after only one treatment period will not be included in the efficacy analyses. If a patient has baseline data missing for a parameter, within a treatment period, data for that patient and parameter will not be derived or analysed for that treatment period.

No imputation of missing data will be performed.

All available data from all dosed patients who have received study treatment will be listed and summarised. Any unscheduled or unplanned readings will be presented within the patient listings, but only the scheduled readings will be used in any summaries. If a treatment day is rescheduled due to variability in FEV_1 or other reason, the rescheduled treatment day will be listed and summarised as the valid treatment day.

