6.18.3 Vital Signs

The AUC parameters will be calculated using the linear trapezoidal rule. The peak pulse rate will be computed as the maximum value in the 4 hours after dosing minus the pre-dose Day 1 baseline value.

Peak (measured in first 4 hours after dosing) and AUC_{0-4h} pulse rate will be derived.

Vital sign observed values and change from baseline by parameter (unit) will be summarised over time.

In addition, 'substantial' changes from baseline will be categorised as follows: change from baseline in systolic/diastolic blood pressure (BP) (systolic BP [>±40 mmHg], diastolic BP [>±20 mmHg]) and pulse rate [>±30 bpm]). The number

and percentage of patients with changes from baseline as categorised above will be summarised separately for positive and negative changes over time and at any postbaseline time point.

All vital sign data will be listed including change from baseline and flags for substantial changes from baseline.,

A listing of clinically significant vital signs recorded throughout the study will be provided.

Mean (±SEM) figures will be presented for changes from baseline blood pressure and pulse rate data for each treatment day. The three study treatments will be represented by different colours on the figures at each postdose timepoint.

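### The count of substantial blood pressure and pulse changes at any time after baseline leaves out unscheduled readings, so it can only err on the low side

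*SAP*

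**What the plan says.** The rule for tables is in SAP 6.4: "Only scheduled post-baseline laboratory, vital signs and ECG values will be tabulated". The next sentence deals with everything else: "Post-baseline repeat/unscheduled assessments will be disregarded, although they will be listed". It goes on to say that those of clinical significance in particular are to be noted. SAP 6.2 puts unscheduled readings in the patient listings and says that "only the scheduled readings will be used in any summaries". Protocol 10.4.8 contains the same rule, so the SAP is following the protocol here.

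SAP 6.18.3 defines substantial changes from baseline as more than 40 mmHg systolic, 20 mmHg diastolic or 30 bpm pulse, in either direction. Patients with such changes are to be "summarised separately for positive and negative changes over time and at any postbaseline time point". SAP 6.18.4 plans QTcF categories (above 450, 480 and 500 msec; increases above 30 and 60 msec). The absolute values go into a shift table over time. The text does not say whether the counts of increases are by time point or across time points.

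Unscheduled readings can arise in any patient, because Protocol 6 allows repeat and unscheduled visits and procedures at the investigator's discretion. For a withdrawn patient judged to need closer supervision, Protocol 4.3 adds that "an unscheduled visit prior to and in addition to the scheduled follow up visit may be performed".

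**The concern.** A count described as covering any time after baseline should use every reading taken after baseline. Under SAP 6.2 and 6.4 it uses only those on the schedule. Unscheduled readings are taken at the investigator's discretion, and a natural reason to take one is that something looked wrong. The excluded readings may therefore include the extreme values the table exists to count.

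Protocol 1.2 names hypotension and tachycardia as the signals from non-clinical work, and these are what the blood pressure and pulse counts would show. Readers comparing treatments will look at the per-treatment counts. A listing does not supply those counts.

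**Working it through.** The plan states no figure for this point, so there is none to reproduce. The check sets the sections side by side, with a little arithmetic for scale.

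1. **Reach of the rule.** SAP 6.2 and 6.4 and Protocol 10.4.8 contain no exception. SAP 6.18.3 and 6.18.4 do not create one.

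2. **Tables affected.** An unscheduled reading belongs to no scheduled time point, so leaving it out of by-time-point means, figures and shift tables is ordinary practice. The any-time count in SAP 6.18.3 is different, because it collapses over time points. The QTcF counts fall in the same class only if they are collapsed too.

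3. **Direction.** For one patient on one treatment, let I(S) = 1 if any scheduled reading crosses the threshold and I(U) = 1 if any unscheduled one does. With all readings, the patient counts if max(I(S), I(U)) = 1, and max(I(S), I(U)) ≥ I(S). The scheduled-only count is therefore never above the all-readings count. The shortfall is the number of patients with I(S) = 0 and I(U) = 1.

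4. **Size.** The documents give no number of unscheduled readings, so the shortfall cannot be estimated. For scale, with the planned maximum of 30 patients, one patient is 1/30 = 3.3 percentage points. If only 24 contributed to a treatment, it would be 1/24 = 4.2 points. The figure of 24 is the evaluable target; safety tables use the safety set.

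5. **Scheduled coverage.** Post-dose vital signs per period (Protocol 7.4.3): 7 on Day 1 + 6 on Day 2 + 7 on Day 3 = 20. Post-dose ECGs per period (Protocol 7.4.5): 2 + 1 + 3 = 6. Vital signs are well covered while a patient stays on schedule; ECGs less so.

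6. **Whether the end of study visit fills the gap.** It takes place 4 to 10 days after Day 4 of Treatment Period 3. Day 4 is 24 hours after the last dose, so for a completer the visit is 5 to 11 days after dosing. Protocol 3.2 takes five half-lives as elimination. With its mean of 10.5 h at 6 mg, 5 × 10.5 = 52.5 h, or 2.2 days. With the upper mean of 13 h in Protocol 1.1, 5 × 13 = 65 h, or 2.7 days. By the protocol's own criterion the visit falls after the drug has gone, so it does not replace a reading taken close to dosing.

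7. **Baseline.** SAP 6.2 defines baseline as the last value before dosing, unscheduled values included. An unscheduled reading can therefore set the reference but can never count as a post-baseline outlier.

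**The case against.** The case for leaving the plan alone is substantial.

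- **The readings are not lost.** They are listed and clinically significant ones noted. SAP 6.18 plans separate listings of abnormal values, SAP 6.18.3 a listing of clinically significant vital signs, and SAP 6.18.4 a listing of abnormal ECGs. With about 30 patients at one centre, these can be read patient by patient. Adverse events, including those leading to discontinuation, are tabulated in their own right. This stands, and it limits the harm. It does not make the any-time count correct.
- **The rule is the protocol's own.** This also stands: a change to it is a change from Protocol 10.4.8 and must be recorded as one.
- **More rechecks give more chances to cross a threshold.** This is true, and it is why both counts should be shown.
- **An unscheduled reading has no time-matched baseline**, which is what SAP 6.2 specifies for ECG and vital signs. This is correct, and any fix must supply a reference.

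A reader might also infer stronger claims that the documents do not support:

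- Unscheduled visits are not the protocol's main route for following withdrawn patients. Protocol 4.3 makes the end of study visit the routine and the extra visit optional.
- The laboratory summaries and planned shift tables are not shown to be distorted. Laboratory values and the ECG shift table are presented over time, and no worst-value shift table is planned.
- An excursion between scheduled ECGs is not detectable only by an unscheduled ECG. A 12-lead Holter runs for at least 24 hours from before the Day 2 dose, and pulse is measured at 20 scheduled times.
- Nothing says that a patient who stops treatment on Day 1 or 2 misses the Day 4 bloods, or that omissions would be more frequent on one treatment.

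**Conclusion.** The point holds for one stated output and conditionally for another. The SAP 6.18.3 any-time counts of substantial blood pressure and pulse changes omit real post-baseline readings, and any resulting error is downward. The QTcF threshold counts in SAP 6.18.4 are affected in the same way only if they are reported across time points, which the text leaves open.

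The direction follows from counting over a subset of readings and assumes that scheduled readings keep the same baseline in both counts. The size is unknown and would be zero if no patient's only extreme value were unscheduled. This is a limited correction to a safety count. It is not evidence that safety data are withheld from the report or that the SAP departs from the protocol.

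**What to change.** Keep scheduled readings only for by-time-point summaries, figures and by-time-point shift tables. Then amend SAP 6.2, 6.4, 6.18.3 and 6.18.4 as follows:

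- The any-post-baseline vital-sign outlier counts, and a new any-time row for the QTcF categories, use all post-dose readings, scheduled and unscheduled.
- Each reading is assigned to a treatment by the period rule that SAP 6.18.1 already uses for adverse events. A value that serves as the next period's baseline is not also counted as post-baseline for the period before.
- The change from baseline of an unscheduled reading is taken from that period's pre-dose Day 1 value, which SAP 6.18.3 already uses for peak pulse rate. Scheduled readings keep their existing reference. Absolute QTcF categories need none.
- The scheduled-only count is shown beside the all-readings count. A footnote says that patients rechecked more often have more chances to cross a threshold.
- SAP 6.19 records the change from Protocol 10.4.8. Protocol 10.1 also requires departures from the protocol analysis to be justified in the study report.

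The cost is SAP wording and minor programming. No new data are needed, because the plan already requires unscheduled readings to be listed.

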6.5 Disposition of patients

The number and percentage of all patients enrolled, randomised, included in the FAS, CAS, SAF, PK analysis set who completed the study and prematurely discontinued study treatment and study duration will be summarised. The number and percentage of patients will be summarised by their reasons for withdrawal where applicable. Eligibility for each of the analysis sets along with reasons for exclusion will be listed. Study completion/withdrawal data will be listed.

6.6 **Protocol Deviations**

Prior to database lock, Verona Pharma Plc may review the individual deviations and classify them as major (which includes those described in section 6.3 above) or minor during a data review meeting (DRM).

Details of all protocol deviations (date, deviation category, specific details and classification of major or minor) and patient eligibility will be listed.

The number and percentage of patients with protocol deviations will be summarized by category.

6.7 Background and Demographic Characteristics

6.7.1 Demography

Demographic characteristics (age, sex, ethnic origin and race), body measurements (height, weight and body mass index (BMI)) and smoking status collected at Screening will be summarised.

Age is calculated in years from the date of first administration of study treatment.

BMI is calculated as (weight (kilogram(kg))/height (m)²).

All patient demographic data including informed consent will be listed.

6.7.2 Medical History

Medical history events will be coded using the latest Medical Dictionary for Regulatory Activities (MedDRA) dictionary version. The number and percentage of patients will be presented by system organ class (SOC), and preferred term (PT), where SOC and PT will be presented in decreasing frequency of the total number of patients with medical history events. All events will be listed, which will include a flag for ongoing conditions.

6.7.3 Diagnosis of COPD

Details of the diagnosis of COPD including date of diagnosis, date of onset of symptoms, any hospitalisations, history of a chronic cough with phlegm for at least 3 months a year for at least 2 years and number of exacerbations in the prior year (defined as needing oral steroids and/or antibiotics) taken at screening will be summarised and listed. Where possible, duration of symptoms (years) will be derived as (date of enrolment – date of symptom +1). Duration of diagnosis (years) will be derived as (date of enrolment – date of diagnosis + 1). Dates will not be imputed, instead, where days and months are missing but year known, duration can be derived from years, where months and year are known, duration can be derived using the month and year.

6.7.4 Pregnancy test

Details of the pregnancy test conducted at Screening, Treatment Period 1 - Day 1, Treatment Period 2 - Day 1, Treatment Period 3 - Day 1 and End of Study will be listed.

6.7.5 Alcohol breath test

Details of the alcohol breath test conducted at Screening will be listed.

6.7.6 Serology

Details of the screen for human immunodeficiency virus (HIV), hepatitis B and hepatitis C conducted at Screening will be listed.

6.7.7 Chest X-Ray

Details of the chest x-ray conducted at Screening will be listed.

6.7.8 Training

Details of the whole-body plethysmography and inhalation training conducted at Screening will be listed.

6.7.9 Spirometry: Reversibility Test

Reversibility in response to salbutamol will be assessed at Screening as an eligibility measure. Spirometry (FEV₁ and FVC) assessment before and after four puffs (400 mcg) of salbutamol administered using a pMDI will be performed.

Three technically acceptable measurements should be made and recorded in the eCRF. Spirometry assessments may be performed up to eight times to obtain three acceptable readings according to ATS guidelines. The highest reading from each assessment will be used for calculation of predicted values and increase from baseline.

The following must be confirmed for inclusion:

• Post-bronchodilator FEV₁/FVC ratio of ≤0.70 (derived as the highest of the 3 post-bronchodilator FEV₁ measurements divided by the highest of the 3 post-bronchodilator FVC measurements)

• Post-bronchodilator FEV₁ ≥40 % and ≤80% of predicted normal*

• Demonstrates \geq 150 mL increase from pre-bronchodilator FEV₁ (derived as the highest of the 3 post-bronchodilator FEV₁ measurements – the highest of the 3 pre-bronchodilator FEV₁ measurements)

*NHANES III will be used as a reference for normal predicted values.

These data will be summarised and listed.

6.8 Prior, Rescue and Concomitant Medications and COPD Therapies

Medications will be coded using the latest World Health Organization Drug dictionary (WHO Drug) version.

Prior therapies and prior medications are defined as those that started and ended prior to the first administration of study treatment. Medications that are ongoing at the first administration of study treatment or started after time of first administration will be deemed to be concomitant medications. If medication dates are incomplete and it is not clear whether the medication was concomitant, it will be assumed to be concomitant.

The following rules will be used for defining whether a medication is concomitant and which treatment they should be assigned to:

- 1. If the start date is after the period first administration of study treatment and before the start of the next period, then the study treatment is concomitant and assigned to the treatment for that period.
- 2. The start date is before the period first administration of study treatment and the end date is after the first administration of study treatment of the period, then the medication is concomitant and assigned to the treatment for that period.
- 3. Any medication taken after the end of the final period (i.e. in the follow-up period) will be concomitant and will be assigned to the treatment for the final period.
- 4. Any medication that starts and ends during the washout period counts as part of the previous treatment period.
- 5. Any medication that starts during the washout period and ends after the start of the next treatment period will be assigned to the previous and current treatment period,

The number and percentage of patients taking prior and separately concomitant medications will be summarised by medication class and standardised medication name, where medication class and standardised medication name will be presented

in decreasing frequency of the total number of patients with medications. In summary tables, patients taking multiple medications in the same medication class or having the same standardised medication recorded multiple times in the study will be counted only once for that specific medication class and standardised medication name.

Medication data will be listed, where concomitant medications will be flagged.

6.9 Lifestyle Restrictions

The date and time of the lifestyle restrictions assessments, information regarding refrain from xanthine for at least 24 hours prior to visit (yes/no), information regarding refrain from alcohol for 24 hours prior to visit (yes/no) and whether the patient refrained from strenuous exercise for 72 hours prior to visit will be listed.

6.10 Administration of Study treatment and Exposure

Study treatment administration will take place at the study centre and will be administered by the investigator or designated and trained study centre personnel.

Patients will be dosed with open label tiotropium DPI 18 mcg (two inhalations from one capsule) followed immediately (within 2 minutes) with either blinded RPL554 or placebo using a nebuliser according to the randomisation scheme. At 12 hours (±30 minutes) after the morning dose, the second dose of RPL554 or placebo will be administered by nebulisation.

A summary of whether treatment was received (yes/no), whether the patient fasted from 2 hours pre-dose, and continue until 2 hours post-dose (yes/no) and has the patient refrained from smoking within 1 hour of dosing (yes/no) will be presented by timepoint and treatment day.

The number of doses of study treatment administered (0 if no treatment administered, 1 if only first or second dose taken and 2 if first and second doses taken) during each period and the number of days of exposure to the study treatment (last date of dosing minus first day of dosing + 1) during each period will be summarised.

The duration of the first and second nebulisation of RPL554 in minutes will be summarised by timepoint and treatment day and listed. Time of tiotropium dosing will be included in the listing.

Details of the first compressor unit number, volume of first residual product (mL), second compressor unit number and volume of second residual product (mL) will be summarised and listed.

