	During each treatment period, patients will be dosed with tiotropium once daily each morning (Day 1 to Day 3) and either RPL554 or placebo twice daily (in the morning and evening) on Day 1 and Day 2 and once in the morning only on Day 3 (total of 5 doses of RPL554 or placebo in each treatment period; there is no evening dose of RPL554 or placebo on Day 3 of each treatment period).
	The pre-dose FEV_1 at Day 1 of Treatment Period 2 and Day 1 of Treatment Period 3 must be within $\pm 20\%$ of the pre-dose FEV_1 at Day 1 of Treatment Period 1, in order to ensure consistent baseline FEV_1 for each study treatment.
	The following provides a brief overview of the major procedures to be performed during each treatment period.
	The following will be performed at Day 1 of each treatment period:
	• Measurements of lung function (FEV ₁ and forced vital capacity [FVC]) by spirometry pre-dose and up to 12 hours post-dose
	• 12-lead electrocardiogram (ECG) pre-dose and up to 4 hours post dose and vital sign (supine) measurements pre-dose and up to 12 hours post-dose
	• Measurement of lung volumes by whole body plethysmography pre-dose
	The following will be performed on Day 2 of each treatment period:
	• Measurement of lung function (FEV ₁ and FVC) by spirometry pre-dose and for up to 4 hours post-dose
	• 12-lead ECG pre-dose and up to 2 hours post dose and vital sign (supine) measurements pre-dose and up to 12 hours post-dose
	• Measurement of lung volumes by whole body plethysmography pre-dose and at 1.25 hours post-dose
	• Holter monitoring pre-dose and up to at least 24 hours post-dose.
	The following will be performed at Day 3 of each treatment period:
	• Measurements of lung function (FEV ₁ and FVC) by spirometry pre-dose and up to 24 hours post-dose
	• 12-lead ECG and vital signs (supine) measurements pre-dose and up to 24 hours post-dose
	• Pharmacokinetic blood sampling pre-dose and up to 24 hours post-dose
	• Laboratory safety tests (haematology and biochemistry) at 24 hours post-dose
	The 24-hour assessments and Holter removal will be performed prior to discharge from the study centre on Day 4.
	Adverse events will be recorded throughout the study.
Number of Patients Planned:	24 evaluable patients (randomise up to 30 patients)

Main Criteria for Eligibility:	Inclusion Criteria

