6.4.2 Study Treatment Administration

Patients will be dosed with open label tiotropium DPI 18 mcg (two inhalations from one capsule) followed immediately (within 2 minutes) with either blinded RPL554 or placebo using a nebuliser according to randomisation scheme. There is no evening dose of study treatment on Day 3 of each period.

6.4.3 **Post-Dose Assessments**

Note: 24 hour assessments will be performed in the morning on Day 4 prior to discharge from the study centre.

- 12-lead ECGs at 2, 4 and 24 hours
- Vital signs at 30 minutes and 1, 2, 4, 6, 8 and 24 hours
- Spirometry at 5, 15 and 30 minutes and 1, 1.5, 2, 4, 6, 8, 12, 15 and 24 hours
- Questioning for adverse events

- Blood samples for pharmacokinetics at 5, 30 and 45 minutes and 1, 1.5, 2, 4, 8, 12, 15 and 24 hours
- Blood sample for laboratory safety tests (haematology and biochemistry) at 24 hours
- Brief physical examination, can be performed any time prior to discharge (Day 4)

The procedures listed above for Treatment Period 1 will be repeated for Treatment Period 2 and Treatment Period 3. Patients will be instructed to return in 7 to 21 days (taken from last dose of study medication on Day 3) for the next visit, or if Treatment Period 3, to return in 4 to 10 days (from Day 4) for the end of study visit.

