2 STUDY OBJECTIVES AND DESIGN

2.1 Study Objectives

The primary objective of the study is to investigate the bronchodilator effect on peak forced expiratory volume in one second (FEV₁) (measured in first 4 hours after dosing) and average (measured as the area under the curve (AUC)) FEV₁ over 12 hours of nebulised RPL554 dosed twice daily for 3 days (five total doses), as compared to placebo, when administered in addition to once daily tiotropium.

The secondary objectives of the study are:

- To investigate the effect of twice daily nebulised doses of RPL554, as compared to placebo, when administered in addition to tiotropium on lung volumes
- To assess the bronchodilator effect on peak FEV₁ (measured in first 4 hours after dosing) and average (measured as the AUC) FEV₁ over 12 hours of nebulised RPL554 after the first dose as compared to placebo, when administered in addition to tiotropium
- To analyse plasma concentrations and assess the steady state pharmacokinetics of RPL554 when administered in addition to tiotropium
- To assess the tolerability and safety of twice daily nebulised doses of RPL554 in addition to tiotropium
- To assess the dose response of two different doses of RPL554 on peak, average (0 to 12 hours), and morning trough FEV_1 on Day 3 when dosed in addition to tiotropium
- To determine the onset of action of RPL554 when administered with tiotropium (after the first dose)
- To investigate the bronchodilator effect on nebulised RPL554, or placebo, administered in addition to tiotropium on average FEV₁ over 4 hours after each morning dose

• To investigate the effects of RPL554 on specific airway conductance (sG_{aw}) and lung volumes (residual volume [RV], functional residual capacity [FRC]) when administered in addition to tiotropium.

The exploratory objectives are:

- To examine the effect of RPL554 on top of tiotropium on average FEV₁ over 24 hours after 3 days of dosing
- To assess morning trough FEV₁ prior to the final dose of study treatment.

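### SAP 6.10 codes doses per period as 0, 1 or 2 although five nebulised doses are planned, so the variable cannot give a patient's dose total for a period

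*SAP*

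**What the plan says.** SAP section 6.10 defines a dose-count variable whose values are 0 for no treatment, then "1 if only first or second dose taken and 2 if first and second doses taken) during each period". The unit is the treatment period and the highest value is 2.

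The planned number is given elsewhere. The protocol synopsis (Study Procedures) states a "total of 5 doses of RPL554 or placebo in each treatment period". Protocol section 6.4.2 adds: "There is no evening dose of study treatment on Day 3 of each period". SAP section 2.1 repeats the figure in the primary objective, where RPL554 is "dosed twice daily for 3 days (five total doses").

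Section 6.10 also shows how it uses the word second: "At 12 hours (±30 minutes) after the morning dose, the second dose of RPL554 or placebo will be administered by nebulisation". The second dose is therefore the evening dose of a treatment day.

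The same section plans other exposure outputs:
- treatment received (yes/no), presented by timepoint and treatment day;
- days of exposure per period, taken as last dosing date minus first dosing date plus 1;
- nebulisation durations, summarised by timepoint and treatment day and listed;
- residual volumes, summarised and listed.

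The SAP's section on changes from the protocol (6.19) does not mention the dose count.

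**The concern.** A count that stops at 2 does not fit a period with five planned doses. A programmer who follows the rule gives the same value to a patient who took everything and to one who missed up to three doses.

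The total matters for interpretation. The primary endpoints are measured after the Day 3 dose, which is the fifth, and protocol section 1.1 says the study doses RPL554 to steady state. Neither the full analysis set nor the completer set in SAP section 6.3 requires a minimum number of doses, and protocol section 10.4.4 plans no formal compliance analysis. A reader who wants to know how many analysed patients had the full regimen in a given period would look to this variable.

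**Working it through.** **Inputs.** Nebulised doses: two on Day 1, two on Day 2, one on Day 3 (protocol synopsis and section 6.4.2). Code: 0, 1 or 2 per period (SAP 6.10). Days of exposure: last date − first date + 1 (SAP 6.10).

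**Step 1: the documents' own figure.** 2 + 2 + 1 = 5 doses per period. This agrees with the synopsis and with SAP section 2.1.

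**Step 2: all possible patterns.** Each of five doses is taken or missed, so there are 2^5 = 32 patterns. By number of doses taken:

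| Doses taken | 0 | 1 | 2 | 3 | 4 | 5 |
|---|---|---|---|---|---|---|
| Patterns | 1 | 5 | 10 | 10 | 5 | 1 |

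**Step 3: literal reading, a count that stops at 2.** Code 0 covers 1 pattern and code 1 covers 5. Code 2 covers 10 + 10 + 5 + 1 = 26 patterns, from two to five doses. Codes 0 and 1 do reveal incomplete dosing; code 2 does not identify full dosing.

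**Step 4: add days of exposure.** A three-day span needs at least one Day 1 dose (3 ways) and the Day 3 dose (1 way), with any Day 2 pattern (4 ways): 3 × 4 × 1 = 12 patterns, all with code 2. By doses taken:
- two doses: 2 patterns
- three doses: 5
- four doses: 4
- five doses: 1

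The sum is 2 + 5 + 4 + 1 = 12. A span under three days shows that something was missed, but a three-day span does not show that everything was taken.

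**Step 5: alternative reading, any morning dose plus any evening dose in the period.** There are three morning doses (2^3 − 1 = 7 ways to take at least one) and two evening doses (2^2 − 1 = 3 ways). Code 2 then covers 7 × 3 = 21 patterns, again from two to five doses.

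**Step 6: per-day reading.** A full period codes as 2, 2, 1, summing to 5. A fully compliant Day 3 then scores 1, the value the rule attaches to a day on which only one of two doses was taken. Section 6.10 states no Day 3 exception and defines no period total.

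**Step 7: does the by-timepoint summary replace the total?** It gives the number of patients who took each scheduled dose, but not how misses group within patients. Suppose two patients are missing at each of two timepoints, 2 + 2 = 4 missed doses. That could be two patients missing two doses each, four missing one each, or three patients (one missing two, two missing one). Only a per-patient count tells these apart.

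**The case against.** The strongest reply is that this is a labelling slip. Section 6.10 uses first and second for the morning and evening doses of a day, so the code is probably a per-day code with the wrong unit. All dosing is supervised at the centre, and protocol section 5.11 requires the date and time of each administration to be recorded. The same section of the SAP summarises treatment received for every timepoint and day and lists the nebulisation data, so missed doses can be found and a patient's total rebuilt by hand. The table shells are in a separate document and may already have the right layout.

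Most of this stands. The per-day reading is the likeliest intent, and the information is not lost from the report. But that reading still needs a Day 3 rule and a period total, and the SAP gives neither. The unseen shells cannot be relied on to correct a derivation that the SAP states differently.

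A reader might go further and infer three things that the documents do not support:
- **That exposure reporting as a whole cannot show full or partial dosing.** It can: codes 0 and 1, spans under three days, the by-timepoint summary and the listings all show missed doses.
- **That exposure is understated by (5 − 2)/5 = 60% in every fully dosed patient.** This ratio holds only for this one variable under the literal per-period reading. It disappears on the per-day reading. Protocol section 10.4.4 estimates RPL554 exposure from residual volume, which the code does not touch.
- **That safety denominators are wrong.** The safety set needs only one administration (SAP 6.3), and adverse event percentages use the number of patients in the analysis set (SAP 6.1). Neither uses the dose count.

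**Conclusion.** The rule is wrong as written: its maximum is 2 against five planned doses, and no reading of it identifies a fully dosed period from a single per-period value. On the literal reading, the top code covers 26 of 32 dosing patterns, or 12 when combined with a three-day span. These are counts of possible patterns, not of patients. With supervised dosing most patients may well receive all five doses, and the documents give no expected rate of missed doses.

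The consequence is limited. What the plan loses is a correct tabulated dose total per patient and period. The primary model, power, type 1 error and analysis sets do not use the variable. The correction is worth making because the rule conflicts with the documents' own figure, is not declared as a change, and is almost free to put right.

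**What to change.** In SAP section 6.10, define the variable as the number of nebulised RPL554 or placebo doses received in each treatment period, range 0 to 5. Summarise it by treatment with the number and percentage of patients receiving all five.

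If the 0/1/2 code is kept, label it per treatment day, state that the Day 3 maximum is 1, and add the period total.

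In either case, say that the count refers to nebulised doses and not to tiotropium. The rule speaks of study treatment, and protocol section 5 uses that term for the inhaler as well.

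The cost is a sentence or two in the SAP and one table shell. Administration dates and times are already collected in the eCRF, so no new data are needed.
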